Appendix 2. Insulin Titration protocol

Basal insulin:

Fasting BG 101-140 mg/dL: continue dose the same

Fasting hyperglycemia (BG 141-180 mg/dL): increase dose by 10%

Fasting hyperglycemia (BG >180): increase dose by 20%.

Fasting BG 70-100 mg/dL: decrease insulin glargine dose by 10%

If patient develops fasting hypoglycemia (BG 60-69 mg/dL), decrease insulin glargine dose by 20%

If patient develops fasting hypoglycemia (BG 40-59 mg/dL), decrease insulin glargine dose by 30%

If patient develops severe fasting hypoglycemia (BG <40 mg/dL) decrease insulin glargine dose by 40%

Correction insulin

Insulin sensitivity factor will be recalculated daily whenever there is a change in insulin dose.

Prandial insulin:

Adjust based on BG levels obtained pre-lunch, presupper, and at bedtime as below for hyperglycemia:

If 2 or more BG levels are 170-190 mg/dL without hypoglycemia, increase dose by 10%

If 2 or more BG levels are 191-230 mg/dL without hypoglycemia, increase dose by 20%

If 2 or more BG levels are 231-250 mg/dL without hypoglycemia, increase dose by 30%

If 2 or more BG levels are >250 mg/dL at separate times of a single day, study team to stop study titration algorithm, recalculate TDD and adjust insulin based on clinical judgement. If any BG 70-100 mg/dL, decrease dose by 20%

If any BG 60-69 mg/dL, decrease dose by 30%

If any BG <60 mg/dL, decrease dose by 50%

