3.2.1 Potential Risks

The potential risks of the study are similar to risks that would be incurred with usual treatment with basal/bolus insulin in the hospital. This includes both hyperglycemia and hypoglycemia, potential allergic reactions to insulin, and pain or bruising at the site of insulin injection. There is also the risk of a loss of confidentiality due to data collection.

Blood samples will be taken during the course of the study as per usual hospital care. In addition, routine point of care blood glucose monitoring through fingersticks by use of standardized bedside glucometers will continue per standard inpatient protocols. There will be no additional blood samples required by the study protocol.

Risks of CGM use include mild discomfort during sensor insertion, along with pain, redness, swelling, minor bleeding and minor infection at the sensor insertion site. Allergic reactions can develop in response to the sensor, the adhesive, and other parts of the CGM. There is a remote chance a sensor wire could break or detach and remain under the skin. Sterile broken or detached sensor wires usually don't pose a significant clinical risk.

Hypoglycemia: The risk of hypoglycemia in insulin-treated non-ICU patients can range from 7-23% in some studies (9, 12). We anticipate that 10-20% of patients receiving insulin during the study may experience hypoglycemia. The number of episodes of hypoglycemia and time spent

in the range of hypoglycemia will be analyzed statistically from CGM-captured data. Hypoglycemia that requires treatment will be defined as a BG < 70 mg/dL.

Hyperglycemia: Quele et al (9) reported that 40% of patients receiving insulin during a hospital stay experienced more than 1 episode of hyperglycemia (BG >300 mg/dL). For patients with \geq 2 blood glucose values >250 mg/dL at separate times of a single day, these subjects will be discontinued from the study insulin titration algorithm and insulin will be adjusted at the discretion of the study team per standard of care.

Procedures for Protecting Against Risks

Hyperglycemia and Hypoglycemia: All glucose results obtained by the bedside glucose meter will be reviewed daily by the study team and insulin will be adjusted according to the study insulin titration protocol (Appendix 2).

Hypoglycemia: Subjects found to have hypoglycemia will be treated according to the hospital practice standard of care.

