For BG <70 mg/dL and patient is able to eat, give 16 g oral glucose, either juice or glucose tabs. Recheck BG in 15 minutes.

For BG <70 mg/dL with altered mental status and/or NPO give 12.5 g of IV dextrose. Recheck BG in 15 minutes, call MD if still <70 mg/dL.

Insulin doses will be decreased as per study insulin titration protocol (Appendix 2) for a BG <70 mg/dL.

Hyperglycemia: Subjects with 2 or more BG >250 mg/dL at separate times in a single day will be removed from the study insulin titration protocol and insulin doses will be titrated as per the discretion of the study team.

Allergy: Patients with a known history of allergy to NovoLog®, Fiasp® or insulin glargine used in the study will be excluded.

Breach of Confidentiality: Only the PI, investigators and study personnel on this project will have access to the master code used to assign subject number. In addition, the investigators will be using password-protected computers and locked cabinets for data storage.

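### Appendix 2's prandial increase rows are non-monotonic: readings of 185/200/240 mg/dL match no row and get no meal-dose increase, while 170/170/120 gets +10%

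*Combined protocol and SAP*

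**What the plan says.** Section 5.1 sends daily insulin titration to Appendix 2. For meal insulin, Appendix 2 says "Adjust based on BG levels obtained pre-lunch, presupper, and at bedtime", followed by three increase rows:

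- "If 2 or more BG levels are 170-190 mg/dL without hypoglycemia, increase dose by 10" per cent
- "If 2 or more BG levels are 191-230 mg/dL without hypoglycemia, increase dose by 20" per cent
- "If 2 or more BG levels are 231-250 mg/dL without hypoglycemia, increase dose by 30" per cent

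A fourth row takes the patient off the table: "If 2 or more BG levels are >250 mg/dL at separate times of a single day, study team to stop study titration algorithm". Decrease rows apply to any single reading of 100 mg/dL or below. Section 3.2.1 matches the fourth row: subjects with two or more readings above 250 in a day "will be removed from the study insulin titration protocol and insulin doses will be titrated as per the discretion of the study team". No row or note covers high readings that fall in different bands.

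The basal rows in the same appendix behave differently. They turn on one fasting value and leave no gaps, for example "Fasting hyperglycemia (BG 141-180 mg/dL): increase dose by 10" per cent, with a further row for everything above 180.

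**The concern.** A titration table should not give less insulin as glucose rises. Here the count of two is applied inside each closed band, so a day with two or three high readings in different bands satisfies none of the rows. The patient's meal dose is then held, although a patient with lower readings would have had it raised. A team that raises the dose anyway departs from the written algorithm.

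At stake are glycemic control on those days and a clear definition of adherence to the algorithm. Prandial dose is itself a secondary outcome (Section 4.3, item 9), and the medical monitor looks at departures from the table (Section 7.12).

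**Working it through.** **Rows applied literally**

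| Day (mg/dL) | Rows met | Meal dose as written | By second-highest reading |
|---|---|---|---|
| 170/170/120 | 170-190 (two readings) | +10% | +10% |
| 185/200/240 | none (one reading per band) | no change | +20% |
| 190/230/250 | none | no change | +20% |
| 200/240/260 | none (only one reading >250) | no change | +30% |

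**How many patterns fall through.** Take five bands: 101-169, 170-190, 191-230, 231-250 and >250.

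- All three readings at 170 or above: 4 × 4 × 4 = 64 ordered patterns. The three bands all differ in 4 × 3 × 2 = 24, and these meet no row.
- Exactly two at 170 or above: 3 × 4 × 4 = 48 patterns. The two bands differ in 3 × 4 × 3 = 36, and these meet no row.
- Together, 60 of 112 patterns meet no row. This counts patterns, not patients.

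**How often, under assumptions.** The documents give no distribution of premeal readings. Assumed: patient means are normal with SD 45 mg/dL (the Section 6.3.7 figure for mean glucose) around 160, 180 or 200; within-day SD is 20, 30, 40 or 50; three rounded readings a day; 600,000 simulated days per combination. A no-row day has a second-highest reading of at least 170, no reading of 100 or below, and no row met.

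| Quantity | Range | Centre (mean 180, within-day SD 30) |
|---|---|---|
| No-row days, share of all days | 8.5-28% | 19% |
| No row and all three readings >180, share of all days | 2.3-8.2% | 5.6% |
| No-row days with at least one reading ≤180 | 54-82% | 70% |
| Mean increase forgone on a no-row day | 15.2-19.7% | 17.6% |

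Of 160 completers at the first titration, 0.085 × 160 = 14 to 0.278 × 160 = 45 would match no row; 0.0225 × 160 = 4 to 0.0822 × 160 = 13 would do so with every reading above 180.

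**Size in units.** Appendix 1 gives half the TDD over three meals and rounds decimals of 0.5 and below down.

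- 80 kg at 0.5 units/kg (assumed weight): TDD 40, meal dose 40/6 = 6.67, rounded to 7. Then +10% = 7.7, given as 8; +20% = 8.4, given as 8; +30% = 9.1, given as 9. The step forgone is 1-2 units.
- 60 kg at 0.5 units/kg: TDD 30, meal dose 30/6 = 5. Then +10% = 5.5, given as 5; +20% = 6; +30% = 6.5, given as 6. The step forgone is 0-1 unit, and it is zero on 30-64% of no-row days.

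**Size in mg/dL, as an upper bound.** With sensitivity factor 1500/TDD, a fraction p of the meal dose is worth p × TDD/6 × 1500/TDD = 250p mg/dL. At the centre, 250 × 0.176 × 0.186 = 8.2 mg/dL averaged over all titrated days (range 3.2-13.7). Meal dosing starts the morning after sensor placement and covers 4-6 meals, so about 1 of 4 to 3 of 6 meals follow the first prandial titration. Over all study meals this gives 0.8-3.4 mg/dL (× 1/4) or 1.6-6.9 mg/dL (× 3/6), ignoring rounding, correction insulin and basal changes.

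**Offsets.** Correction insulin starts at 2 units from 150 mg/dL premeal (Section 5.1, Appendix 1). On every no-row day at least one of the pre-lunch and presupper readings is 170 or above, so it is triggered; both are at least 150 on 72-93% of such days. A fasting reading from the same model exceeds 140, and so raises basal insulin, on 80-98%.

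**The case against.** The strongest objection is that little follows from the gap. The rule is the same in both arms, and essentially one prandial titration matters per patient. A patient at 185/200/240 already receives at least 2 units of correction at lunch and supper, as much as the missed step in the 80-kg example. A higher meal dose would lower later readings and so reduce correction, which makes the net loss smaller than the figures above. Most no-row days include a reading of 180 or below, and with small doses rounding removes the 10% step altogether. Section 7.12 also has a monitor outside the study team look for excessive deviation from the titration protocol after 10 and 40 patients. All of this stands and limits the size of the point. It does not close the gap: correction is given whether or not the meal dose is raised, and the monitor does not supply the missing row.

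Two readings of the text might rescue the rule. Staff could treat each band as open above its lower limit, which would remove the inversion, but the text states closed bands. They could pool readings over days, since the three increase rows lack the single-day wording of the >250 row. Daily titration on three named readings makes one day the natural unit, and at the first titration there is only one day of meal dosing to use.

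A reader might also infer that the study team can simply use judgement on such days. For hyperglycemia, Section 3.2.1 and Appendix 2 grant that only at two or more readings above 250 in a day, so even 200/240/260 is not released.

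**Conclusion.** The point holds as a defect in a dosing rule: followed exactly, the table gives a higher-glucose day no increase and a milder day +10%. The two example days need no assumption beyond the literal text. The frequencies rest on the assumed glucose distributions, and the mg/dL figures are upper bounds. The practical effect is small: about 8-28% of titration days, 2-8% with all three readings above 180, and typically 0-2 units per meal.

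A reader might infer that this biases the Fiasp-NovoLog comparison or undermines the sample size. The documents do not support that, because the written rule is identical in both arms and enters no power calculation. The trial is open-label, so ad hoc decisions on no-row days could in principle differ by arm, but nothing in the documents shows that they do. Nor can the headline range be read as that many patients left badly uncontrolled: most of those days are mild, and correction and basal insulin still act.

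**What to change.** If enough enrolment remains, replace the increase rows with one rule. Take the second-highest of the day's pre-lunch, presupper and bedtime readings: 170-190 gives +10%, 191-230 gives +20%, 231-250 gives +30%, and above 250 leaves the algorithm. State that any reading of 100 or below cancels an increase; this also settles days such as 90/200/210, which now meet both an increase and a decrease row (under 1% of simulated days). When two of three readings share a band, the second-highest always lies in that band, so every increase the table now orders without such a conflict is unchanged. Only the gaps are filled, with steps the table already orders at the same or lower glucose.

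The cost is an IRB-approved amendment of one appendix (Section 7.4) and a small rise in hypoglycemia risk that the documents do not allow anyone to quantify. Timing matters. The document is dated 11/11/2022 and Section 7.15 expects data collection to finish by the end of 2022, so a late change would put two titration rules in one trial. If enrolment is nearly complete, keep the rule. The team could then count, by arm, the days that matched no row and the days on which the dose departed from the table. This is descriptive only and needs no new measurements, since "All glucose results obtained by the bedside glucose meter will be reviewed daily by the study team".

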Appendix 3. Prescreening form

- 1. Primary language: English _____ Spanish _____ Other _____ cannot determine _____
- 2. Located on non-intensive care unit: _____ (Y/N)
- 3. Age 21-80: _____ (Y/N)
- 4. Patient pregnant/breastfeed: _____ (Y/N/unknown)
- 5. Serum creatinine $\geq 2 \text{ mg/dL}$: _____(Y/N)
- 6. History type 2 diabetes prior to admission: _____ (Y/N)
- 7. Outpatient medications:
 - a. HbA1c of \geq 8% on \geq 1 oral or injectable agent: _____ (Y/N)
 - b. Insulin: _____ (Y/N)
 - c. 2 oral agents: ____ (Y/N)
 - d. Insulin dose >1 unit/kg/day: _____(Y/N)
- 8. Discharge planned within 48 hours: _____ (Y/N)
- 9. BMI <45: _____ (Y/N)
- 10. History of type 1 diabetes or LADA (late-onset autoimmune diabetes): _____ (Y/N)
- 11. History of gastroparesis or cirrhosis: _____ (Y/N)
- 12. Currently on glucocorticoids OR plan for treatment with glucocorticoids within the next 72 hours.(prednisone, dexamethasone, methylprednisolone, hydrocortisone): _____ (Y/N)
- 13. Admission diagnosis of diabetic ketoacidosis, hyperglycemic hyperosmolar syndrome, solid organ transplantation, or coronary artery bypass surgery: _____ (Y/N)
- 14. Receiving tube feeds or total parenteral nutrition: (Y/N)
- 15. Expected to be NPO for >24 hours: _____ (Y/N)
- 16. Receiving > 1 gram of acetaminophen or hydroxyurea in the hospital: _____ (Y/N)
- 17. Using insulin pump or continuous glucose monitoring device in the hospital: _____ (Y/N)
- 18. Currently incarcerated: _____ (Y/N)
- 19. Allergy to insulin: _____ (Y/N)
- Tested positive for SARS-CoV-2 (severe acute respiratory syndrome coronavirus 2) OR there is an ongoing clinical suspicion for COVID-19 infection in spite of a negative test: _____(Y/N)

Appendix 4. Patient Reported Outcome (PRO) Questionnaire

Instructions:

A Patient Reported Outcome (PRO) questionnaire is being included in this trial to obtain information about the acceptability of wearing a continuous glucose monitoring device while in the hospital.

When should the PRO questionnaire be administered?

At completion of the study. It takes approximately 5 minutes.

Before giving the PRO questionnaire to the subject

Fill in the header on each page

Giving the PRO questionnaire to the subject

-Explain that the questionnaire assesses the subject's perception of wearing a continuous glucose monitoring device in the hospital

-Explain that the subject should answer the questions him-/herself, without assistance from family, friends or medical staff

-Encourage the subject to answer every question to the best of his/her ability

-Ask the subject to select only one answer for each question

-Ask the subject to refrain from writing any extraneous comments in the questionnaire -Explain to the subject that the completed questionnaire will be reviewed for any written comments that may suggest issues with wearing the continuous glucose monitoring device

Completion of the PRO questionnaire

-Ensure that a staff member is accessible if questions arises

-If interpretive questions arise, ask the subject to read the question again and answer based on what he/she thinks the question means

-if the subject accidentally marks an incorrect response, ask him/her to strike it out with a single line and mark the correct response instead

After completion of the PRO questionnaire

-Collect the completed questionnaire from the subject

-Review them for potential adverse events and document the review on the designated signature sheet

-File the completed questionnaires in the trial file.

Questionnaire:

Trial ID:	Subject number:	Date: (DD/MMM/YYY):
Dear Study Participant,		
Please complete the quyou have reported any satisfied you are with v remain confidential. Th treated anonymously. monitoring device in th	estions on the following pages. The adverse effects with wearing the cor vearing it. Any adverse events will b ney will be compiled with the respon The data will be used to better unde e hospital.	study staff will review your answers to see if ntinuous glucose monitoring device, and how e reported. Otherwise, your responses ses from the other study participants and rstand the experience of wearing a glucose

1. When the sensor was applied, Image: Constraint of the sensor was applied, how much discomfort did you notice? Image: Constraint of the sensor was applied, how much discomfort did you notice? Image: Constraint of the sensor for several hours, how much 3. After you had been wearing the sensor for several hours, how much Image: Constraint of the sensor for several hours, how much discomfort did you notice? Image: Constraint of the following problems wearing the sensor: Sensor falling off? Yes A. Did you experience any of the following problems wearing the sensor: Sensor falling off? Yes No If yes, how bothersome If yes, how bothersome Image: Image: Image: Constraint of the sensor, would you prefer to use the sensor to measure your blood sugar instead of having a fingerstick checked while in the hospital? Yes No S. Based on your experience wearing the senor, would you prefer to use the sensor to measure your blood sugar instead of having a fingerstick checked while in the hospital?		Not at all easy	Somewhat easy	Very easy	
None Mild Moderate Severe 2. When the sensor was applied, how much discomfort did you notice? Image: Severe intermed i	1. When the sensor was applied, how easy or difficult was this?				
 how much discomfort did you notice? a. After you had been wearing the sensor for several hours, how much a. After you had been wearing the sensor for several hours, how much biscomfort did you notice? 4. Did you experience any of the following problems wearing the sensor: Sensor falling off? Yes No Skin irritation at the site of the sensor? Yes No If yes, how bothersome mild moderate severe 5. Based on your experience wearing the senor, would you prefer to use the sensor to measure your blood sugar instead of having a fingerstick checked while in the hospital? Yes No 6. Based on your experience wearing the senor, would you prefer to use the sensor to measure your blood sugar instead of having a fingerstick checked while at home? Yes No 	2 When the sensor was applied	None	Mild	Moderate	Severe
